## 1. Study Protocol

In this study, a double-blind randomized experimental design was used to allow subjects to take six months of health supplements (experimental group) and six months of placebo (control group) to see their effects on fatty liver, liver fibrosis and metabolic indicators.

First ask the patient to agree to participate in the trial and fully understand the content of the project. After the eligible subjects are evaluated and confirmed to be able to participate in the trial, they will take health care products daily according to the research setting (3 tablets before breakfast, 3 tablets before dinner, total 6 tablets ), at the first time of the test, 4 weeks, 8 weeks, 12 weeks, 16 weeks, and 24 weeks respectively to check blood and biochemical values, including creatinine (Cr), liver function index (AST, ALT), pre-meal blood sugar (AC) , And use Fibroscan to detect fatty liver and liver fibrosis. At the first time of the test, 4 weeks, 12 weeks, 12 weeks, 12 weeks, and 24 weeks, return to check blood routine / white blood cell classification examination (CBC/DC), uric acid (UA), cholesterol blood fat (HDL, LDL), triglyceride (TG), lipid Adiponectin/Leptin (Adiponectin/Leptin), C-reactive protein (CRP), insulin (Insulin); In addition, at the first, 12 weeks, and 24 weeks of the test, the metabolic indicators related to glycosylated hemoglobin (HbA1c) were tested.

This study will extract the follow-up data of subjects' return visits for analysis and research. The follow-up methods are phone reminders two weeks before the start of the trial, and reminders during monthly visits, asking about taking status, etc., to increase the subjects' compliance.

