## 2. Study procedures

Evaluation Procedure	Regist ration	First Time	Week 4	Week 8	Week 12	Week 16	Week 24
Informed Consent	v	Α					
		B		2.		25	
Assess Eligibility	v	Α	8	5		2	
		B					
Blood inspect							
Cr 、 AST 、 ALT 、 AC CBC/DC 、 UA 、 HDL 、 LDL 、 TG 、 Adiponectin /leptin 、 CRP 、 Insulin		Α	Α	Α	Α	Α	Α
		B	В	В	В	В	В
		A	А		А		А
		В	В		В		В
HbA1c		Α			Α	-	Α
		В		5	B	2	В
FibroScan		Α	Α	Α	Α	Α	Α
		B	В	В	В	В	В

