#### SCHEDULE OF EVENTS

## 3. Statistical Analysis Plan

This study is expected to include a total of 60 people with non-alcoholic fatty liver disease, divided into two groups, 30 people in each group, double-blind randomized test. The primary end point (primary end point) is to see the severity of changes in the patient's steatohepatitis and fibrosis. The secondary end point is the degree of change in the patient's weight and lipid profile. Continuous variables are presented in normal probability plots and Shapiro-Wilk test evaluation. The relationship between variables Connectivity is analyzed by Pearson's correlation, and the Intra-intervention comparison is performed by Paired t test. Unify The calculation software is based on R software version 2.11.1.

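### The secondary end point combines at least four outcomes, sets no deciding visit, and is tested only by before-after comparison within an arm

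*Combined protocol and SAP*

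**What the plan says.** Section 3 (Statistical Analysis Plan) states: "The secondary end point is the degree of change in the patient's weight and lipid profile". It defines no composite, names no deciding component or visit, and does not say how the degree of change is to be expressed.

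Section 1 (Study Protocol) lists the lipids as "cholesterol blood fat (HDL, LDL), triglyceride (TG"), which gives three fractions. The visit list for that blood panel is garbled: "At the first time of the test, 4 weeks, 12 weeks, 12 weeks, 12 weeks, and 24 weeks". In the Section 2 table two blood-test rows have run together, but one set of marks falls at the first visit and weeks 4, 12 and 24. Those are the visits on which text and table agree for the lipids. Weight is listed neither in the Section 1 assessments nor in the Section 2 table.

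The only test of change in Section 3 is this: "the Intra-intervention comparison is performed by Paired t test". The section also names normality checks and Pearson correlation. It gives no between-group test, significance level, order of testing, multiplicity rule or exploratory label. The design is nevertheless a randomised comparison with placebo: "divided into two groups, 30 people in each group, double-blind randomized test".

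**The concern.** Two gaps meet in one sentence of the SAP.

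- **The comparison.** Section 1 asks what the supplement does, with a placebo group as control. A paired t test within the supplement arm asks whether values moved from the first visit. They can move with no supplement effect, through regression to the mean or because trial participants change their habits. The placebo arm is there to remove such movement, and a within-arm test does not use it.
- **The choice.** Several outcomes and visits sit under one label and nothing says which decides. Whoever writes the report can pick the fraction and visit after seeing the data.

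What is at stake is whether any statement about lipids or weight in the final report can be attributed to the supplement.

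**Working it through.** **Inputs from the documents.** 30 people per group (Section 3); three lipid fractions (Section 1); three post-baseline lipid visits (Sections 1 and 2, on the reading above); a within-arm paired t test (Section 3).

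**Inputs assumed.** Two-sided 5% per test, since no level is stated. Correlation between change scores of 0 to 0.8, since none is given. The four-outcome line also assumes that weight is measured at that one visit.

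**The plan's own figure.** The total of 60 cannot be reproduced, because no power, effect size, standard deviation or dropout is stated. For orientation, the normal approximation puts the difference detectable with 80% power at two-sided 5% at (1.960 + 0.842) × √(2/30) = 0.72 SD.

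**Step 1: what a paired test in one arm responds to.** With n = 30 the critical t on 29 degrees of freedom is 2.045. The test is therefore significant once the mean change exceeds 2.045/√30 = 0.37 SD of the change scores. If everyone, in both arms alike, drifted by an amount d for reasons unrelated to the supplement, the non-central t distribution gives the chance of p<0.05 in the supplement arm for one outcome at one visit:

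| Common drift d (SD of change) | Chance of p<0.05 |
|---|---|
| 0 | 5% |
| 0.1 | 8% |
| 0.2 | 19% |
| 0.37 | 51% |

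The drift values are illustrative; the documents give none. A between-arm test stays at 5% in every row, because the same drift cancels.

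**Step 2: several tests, no change at all.** For m independent tests the chance of at least one p<0.05 is 1 − 0.95^m:

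- m = 3: 1 − 0.857 = 14.3%
- m = 4: 1 − 0.815 = 18.5%
- m = 9: 1 − 0.630 = 37.0%

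Correlation lowers this. A simulation (20,000 replicates, normal change scores with equal correlation, n = 30, paired t tests in one arm) gives:

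| Tests counted | Corr. 0 | Corr. 0.5 | Corr. 0.8 |
|---|---|---|---|
| 3 lipids, week 24 only (m = 3) | 14.6% | 12.9% | 10.3% |
| 4 outcomes, one visit (m = 4) | 18.8% | 15.7% | 11.7% |
| 3 lipids × 3 visits (m = 9) | 37.1% | 27.3% | 17.0% |

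A repeat run agreed to within one percentage point.

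**Step 3: what each remedy does.** Comparing arms removes the problem in Step 1 but not that in Step 2: four between-arm tests at correlation 0.5 still give about 15%. Testing each of the four at 0.05/4 = 0.0125, which is Holm's first step, brings the simulated rate at correlation 0.5 to 4.5%.

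**The case against.** **Silence is not permission.** A reader might infer that the plan allows a secondary benefit to be claimed from any single nominally significant result. The documents do not say that. Section 3 states no significance level, success rule or claim rule, and speaks of the degree of change, which is descriptive wording. What stands is that nothing prevents such a reading.

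**Twelve tests is too many.** One might multiply four outcomes by three visits. That would need weight at weeks 4, 12 and 24, and the documents schedule weight at no visit. The visit count that can be supported is for the lipids alone.

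**The Step 2 rates are not false-positive rates for a supplement effect.** This is right. They assume no within-arm change and count one arm. Under the plan as written, the chance of wrongly crediting the supplement depends on an unknown background drift, as Step 1 shows, and no multiplicity adjustment repairs that.

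**A between-arm comparison may be intended.** The randomised placebo design makes that plausible. Even so, the SAP names no method for it.

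**Unadjusted secondary outcomes are common.** In a 60-person trial, estimates with intervals and no adjustment are defensible. The choice between adjustment and an exploratory label is a trade-off, and lack of adjustment alone would be a minor point.

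**Week 24 is the natural end point.** Treatment lasts six months, so week 24 is the obvious final assessment. The plan does not say that it decides, but on that reading the relevant range is 10-15% for the lipids, or 12-19% with weight.

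**Conclusion.** The concern holds as a gap in both the comparison and the definition. The secondary end point is at least four outcomes with no deciding visit, and the one stated test of change cannot separate a supplement effect from a change that would have happened anyway. The within-arm test is the more serious fault; the multiplicity adds to it.

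With no change at all, the chance of at least one nominally significant result in one arm is two to three times the nominal level at week 24 (10.3/5 = 2.1 to 14.6/5 = 2.9 for the three lipids). Over three visits it is three to seven times (17.0/5 = 3.4 to 37.1/5 = 7.4). These figures rest on an assumed two-sided 5%, assumed correlations of 0 to 0.8, and the weeks 4, 12 and 24 reading of the lipid visits.

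The sponsor should correct this before unblinding. It limits what can be said about weight and lipids and does not bear on the primary end point.

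**What to change.** Replace the secondary end point sentence in Section 3 with wording such as:

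> The secondary outcomes are the changes from first visit to week 24 in LDL, TG, HDL and weight. Each is compared between supplement and placebo by analysis of covariance adjusted for the first-visit value, and reported as a difference with 95% confidence interval. Results at weeks 4 and 12, and within-arm paired tests, are descriptive.

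Then add one of two sentences; the choice is the sponsor's:

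- the four p-values are adjusted together by Holm's method at two-sided 5%; or
- all secondary results are exploratory, and no claim of a secondary effect will be made.

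Add weight at the first visit and week 24 to the Section 1 text and the Section 2 table. Correct the repeated week 12 in the Section 1 visit list at the same time.

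**Cost.** For the lipids this is SAP wording only, using samples already planned. Weight needs one routine entry at two existing visits. Fewer secondary results will reach nominal significance. Under Holm the smallest of the four p-values faces 0.0125. For an outcome with a true difference of 0.72 SD, power at that threshold is about 62%, against 80% at 5% (Φ(2.802 − 2.498) = Φ(0.304) = 0.62). The exploratory label avoids that loss but gives up a confirmatory secondary claim.

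### Change in body weight is part of the secondary endpoint, but no weight measurement is specified at any of the six assessment times

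*Combined protocol and SAP*

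**What the plan says.** - **Endpoint (Section 3, Statistical Analysis Plan).** "The secondary end point is the degree of change" in "weight and lipid profile". The planned size is "30 people in each group", 60 in total. Neither the interval nor the form of the weight change is given.
- **Analysis (Section 3).** The only comparison named is within arm: "Intra-intervention comparison is performed by Paired t test".
- **Visit text (Section 1, Study Protocol).** Participants return "to check blood and biochemical values, including creatinine (Cr), liver function index (AST, ALT), pre-meal blood sugar (AC"), with FibroScan, at six times: First Time and weeks 4, 8, 12, 16 and 24. A second blood panel includes "cholesterol blood fat (HDL, LDL), triglyceride (TG"). HbA1c is taken at First Time and weeks 12 and 24.
- **Schedule table (Section 2, Study procedures).** The rows cover informed consent, eligibility, blood tests, HbA1c and FibroScan. There is no row for weight or any other body measurement.
- **Other contact (Section 1).** The follow-up sentence mentions "reminders during monthly visits, asking about taking status", with an open-ended close, for the purpose of improving compliance. It names no weighing.

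**The concern.** A change endpoint needs at least two values per participant, one of them before the first dose. A site that followed Sections 1 and 2 exactly would record neither weight, so this component could not be derived from the assessments as written. Whether it can be analysed, and over what interval, would depend on practice that the plan does not describe. Sites or staff could weigh at different visits or not at all, and the analysis time point could be chosen after the data are seen.

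The loss would be permanent for anyone dosed without a weight. The named analysis does not help: a paired t test cannot run without both values, and with both it describes change within an arm and does not estimate the difference between supplement and placebo.

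**Working it through.** The plan gives no figure of its own to reproduce here. The check is a count of what is scheduled, set against what the endpoint needs.

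**Assessment times.** Section 1 text and Section 2 table: First Time and weeks 4, 8, 12, 16 and 24, so 6 times. The Registration column that precedes them has no weight entry either.

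**Item-visits per participant** (measurements × times):

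| Measurements | Number | Times | Item-visits |
|---|---|---|---|
| Cr, AST, ALT, AC | 4 | 6 | 24 |
| CBC/DC, UA, HDL, LDL, TG, adiponectin, leptin, CRP, insulin | 9 | 4 | 36 |
| HbA1c | 1 | 3 | 3 |
| FibroScan | 1 | 6 | 6 |
| **Total** | **15** | | **69** |
| Weight | 0 | 0 | 0 |

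CBC/DC is counted as one measurement, and adiponectin and leptin as two. Another way of counting would change 15 and 69 but not the zero for weight.

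**Lipid times.** The Section 1 list for this panel has six entries but prints week 12 three times. Counted once, the distinct times are First Time and weeks 4, 12 and 24, so 4 of 6. In the table as extracted, the two blood panels share one merged label. One pair of rows is marked at all six times and the other at four, and those four are the same as in the text. Assigning lipids to the four-time rows therefore relies on the text.

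**Weights needed against weights specified.**

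- Needed per arm: 2 × 30 = 60
- Needed in total: 2 × 60 = 120
- Specified: 0
- For contrast, lipid panels scheduled at full attendance: 4 × 60 = 240

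**Could a weight row have been lost in extraction?** This is unlikely. The surviving table rows match the tests named in the running text, and that text omits weight independently.

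**The case against.** The strongest reply is that silence shows weight to be unspecified, not unmeasured. The document is a three-section summary. Its lists are essentially lists of laboratory tests plus FibroScan, and weighing is routine enough to go unmentioned. An eligibility assessment is scheduled without its content being given, so it may include a weight. Section 1 also says that follow-up data from participants' "return visits for analysis and research" will be extracted, which is a plausible route for weights recorded at visits.

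Part of this stands. The document does not exclude weighing; this is an omission and not a contradiction, and the irrecoverable baseline is a risk, not an established loss. But the extraction sentence names no variable and no time, and the monthly-visit sentence concerns reminders and compliance. Even if eligibility included a weight, no later weight is specified, so a change would still not be secured.

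It is also fair to say that the missing between-arm comparison applies to every endpoint and is not caused by the missing measurement. It is still correct for this endpoint, and it belongs in the remedy because scheduling weight would not by itself produce a comparison of the arms. Baseline adjustment is the preferred form, although an unadjusted comparison of changes would also compare the arms. Finally, the 4 of 6 for lipids combines a list containing a repetition with a damaged table. It is the likely reading, and the finding on weight does not depend on it.

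**Conclusion.** The concern holds and should be fixed. Weight is specified at 0 of 6 assessment times although its change is part of the secondary endpoint, and 0 of the minimum 120 weights are requested. The effect is confined to one component of the secondary endpoint; the primary endpoint, the FibroScan schedule and the lipid data are not affected. No loss of power is claimed, because the document does not say which weights, if any, would be recorded.

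The conclusion rests on the visit text and schedule table being complete as listed. The figure of 120 assumes two weights for each of the 60 planned participants.

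**What to change.** 1. Add body weight for both groups at First Time, before the first dose, and at week 24, in both the Section 1 visit text and the Section 2 table.
2. In Section 3, define this component as change in weight from First Time to week 24, compared between arms with adjustment for First Time weight, in place of relying only on the within-arm paired t test.
3. If weight will not be collected, delete it from the secondary endpoint.

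The cost of steps 1 and 2 is one simple measurement at two visits participants already attend, 120 weighings in all, plus edits to the visit text, the table and the endpoint and analysis wording. Any participant already dosed without a recorded First Time weight will stay missing for this component and should be reported as such.

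### The only planned test of change is a paired t test within each arm; no analysis compares supplement with placebo

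*Combined protocol and SAP*

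**What the plan says.** Section 1 (Study Protocol) describes a double-blind randomised design in which subjects are "to take six months of health supplements (experimental group) and six months of placebo (control group) to see their effects on fatty liver", with liver fibrosis and metabolic indicators as further targets. Section 3 (Statistical Analysis Plan) plans 60 people, "divided into two groups, 30 people in each group, double-blind randomized test".

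The primary end point "is to see the severity of changes in the patient's steatohepatitis and fibrosis". For the secondary, "The secondary end point is the degree of change in the patient's weight and lipid profile". Neither is worded as a difference between arms, and neither names a time point.

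Section 3 names three methods:
- normal probability plots with the Shapiro-Wilk test, to assess distributions;
- Pearson's correlation, for relationships between variables;
- for change, "the Intra-intervention comparison is performed by Paired t test".

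No alpha, sidedness, power or success rule is given.

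**The concern.** Randomisation and a placebo group allow change on supplement to be set against change without it. A paired t test within an arm makes no use of that. It tests whether the arm's mean change is zero, and the change may come from follow-up, time or regression to the mean as well as from the product.

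Such a shared change is plausible here. The schedule in section 2 lists A and B at the same visits. Section 1 describes "phone reminders two weeks before the start of the trial, and reminders during monthly visits" without distinguishing between groups. The documents do not say how large a shared change might be, but the planned test could not separate it from a supplement effect.

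Running the paired test in both arms and comparing the two p values does not help. A significant result on supplement and a non-significant one on placebo is not a test of the difference. With no success rule in the plan, nothing stops that pattern being reported as efficacy.

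**Working it through.** **Step 1. Is there a between-arm test anywhere?** Shapiro-Wilk tests normality, Pearson's correlation relates variables to each other, and the paired t test is described as within intervention. Sections 1 and 2 add no analysis. No two-sample test, ANCOVA, mixed model or other contrast of supplement with placebo appears.

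**Step 2. Could the paired test itself be the treatment comparison?**
- *Crossover.* This would need each person to take both products. Section 1 labels an experimental and a control group, the schedule ends at week 24 (one six-month period, not two), and section 3 calls the comparison within intervention. This reading does not fit.
- *Intra written for inter.* The paired test would then be applied to two groups of different people, with no matching described. The plan would still need correcting.

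**Step 3. What could follow?** The documents give 30 per arm (30 + 30 = 60). The remaining inputs are assumptions: two-sided alpha 0.05, independent arms, normally distributed changes, no dropout, no supplement effect, and the same mean improvement d (in SDs of change) in both arms.

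For one arm, the paired t statistic is noncentral t with 29 df and noncentrality d × √30; the critical value is 2.045. Let p be the probability of a favourable significant result on supplement. Because the arms are independent, the probability of that result together with a non-significant placebo arm is about p(1 − p). At d = 0.3 this is 0.355 × 0.645 = 0.229.

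| Shared change d | d × √30 | p | Supplement significant, placebo not |
|---|---|---|---|
| 0 | 0 | 0.025 | 0.024 |
| 0.2 | 1.10 | 0.184 | 0.150 |
| 0.3 | 1.64 | 0.355 | 0.229 |
| 0.4 | 2.19 | 0.563 | 0.246 |
| 0.5 | 2.74 | 0.754 | 0.186 |

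In simulation (200,000 trials per value of d), a two-sample t test on change rejected two-sided in 4.9% to 5.0% at every d, or about 2.5% in the supplement's favour. ANCOVA (20,000 trials per setting; baseline-to-follow-up correlation 0.4, 0.6 or 0.8; shared change 0, 0.2 or 0.5) rejected in 4.8% to 5.1%.

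**Step 4. Thresholds for significance.**
- Within one arm: 2.045 / √30 = 0.373 SD of change, whatever placebo did.
- Between arms: 2.002 × √(2/30) = 0.517 SD.

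**Step 5. Two-part primary end point.** Take two measures, each tested within the supplement arm. The chance that at least one is favourably significant is 25% to 33% at d = 0.2 and 84% to 94% at d = 0.5, for an assumed correlation between measures from 0.8 down to 0. At zero correlation: 1 − (1 − 0.184)² = 0.334 and 1 − (1 − 0.754)² = 0.939.

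**The case against.** The best defence is that a between-arm comparison was intended and dropped out of a one-paragraph summary in rough English. Section 1 does state a placebo-controlled aim. That may be so, but a primary analysis that is not written down can be chosen after the data are seen. The finding concerns the written plan, not the sponsor's intent.

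Four narrower points stand in part:
- *Design.* Two groups of 30 would not by itself exclude a two-sequence crossover, and A and B are never defined in the schedule. The case for a parallel design rests on the group labels, the week 24 end and the within-intervention wording, which together suffice.
- *Inference.* The plan does not say which visits are paired, and equal handling of the arms is inferred from the schedule and from the absence of any stated difference. Both are reasonable readings, not text.
- *Numbers.* Alpha, normality and the size of any shared change are assumed. The percentages show what could happen, not what is likely in this trial.
- *Power.* Replacing the test does not make the trial well powered. At 30 per arm, a two-sample test on change has about 48% power for a difference of 0.5 SD, and 80% power needs about 0.74 SD. The plan gives no sample-size justification.

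None of these supplies the missing comparison.

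**Conclusion.** The concern holds, and the plan must be corrected before analysis. As written, it leaves the randomised question untested. This is a wrong primary analysis, not a preference among valid methods. That conclusion comes from the text of section 3 and needs no numerical assumption.

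The size is illustrative. Under the stated assumptions, a shared improvement of 0.2 to 0.5 SD makes the supplement arm favourably significant in 18% to 75% of trials with no supplement effect. The misleading pattern of significance on supplement only arises in 15% to 25%.

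**What to change.** Keep the Pearson clause and replace the paired-t clause with wording such as:

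> The primary analysis compares supplement with placebo at week 24 by ANCOVA, with treatment arm and the baseline value as covariates, for each FibroScan measure (fatty liver and fibrosis). It reports the adjusted between-arm difference, its 95% CI and the two-sided p value. One measure is named as primary in advance, or multiplicity across the two is controlled. The same model is used for the lipid end points, and for weight if recorded at baseline and week 24. Within-arm paired t tests are descriptive and support no efficacy claim.

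**Choices to confirm.** Week 24 is proposed because it is the last scheduled visit; the plan names no primary time point. Section 1 says the study will "use Fibroscan to detect fatty liver and liver fibrosis", so the sponsor should confirm that the FibroScan fatty-liver measure is what section 3 means by steatohepatitis. Multiplicity needs a rule because two between-arm tests, each at 0.05, give a family-wise error of 7.8% to 9.8% (assumed correlation 0.8 down to 0). The analysis population and the handling of missing data should be stated alongside.

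**Alternatives.** A two-sample test on change, or a repeated-measures model over the six FibroScan visits, would also restore validity. ANCOVA is suggested for precision. With equal baseline and week 24 variances, its variance relative to change scores is (1 + r)/2, which is 0.70 to 0.90 for assumed r of 0.4 to 0.8. The difference detectable with 80% power falls from 0.74 SD of change to about 0.74 × √0.70 = 0.62 up to 0.74 × √0.90 = 0.70.

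**Cost.** Wording only for FibroScan and lipids, which are already measured at the first visit and week 24. Weight is a secondary end point but is absent from the measurements in section 1 and the schedule in section 2, so its collection must be confirmed or added. Validity needs no extra patients or visits; whether 30 per arm is enough is a separate question for the sponsor.

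### The SAP's only analysis of change is a paired t test within each intervention: it does not compare supplement with placebo, and response-related dropout can bias it in either direction

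*Combined protocol and SAP*

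**What the plan says.** Section 3 (Statistical Analysis Plan) lists a distribution check (normal plots and the Shapiro-Wilk test), Pearson's correlation, and one analysis of change: "the Intra-intervention comparison is performed by Paired t test". It does not say which two visits form the pair, who is analysed, or what is done about missing readings. No section names a comparison of the arms. The sample is "divided into two groups, 30 people in each group", and the primary end point concerns change in "steatohepatitis and fibrosis".

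Section 1 (Study Protocol) describes a double-blind randomised study of a supplement against placebo. Blood tests and scans are scheduled "at the first time of the test, 4 weeks, 8 weeks, 12 weeks, 16 weeks, and 24 weeks respectively", and the study will "use Fibroscan to detect fatty liver and liver fibrosis". The table in section 2 agrees: both arms have a FibroScan at all six visits. Section 1 also says that data will be taken from subjects' "return visits for analysis and research", and it supports compliance with telephone calls and "reminders during monthly visits, asking about taking status".

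**The concern.** Two problems meet in one sentence of the SAP.

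First, a paired test inside an arm measures change over time in that arm. It does not estimate the difference between supplement and placebo, which is what the randomised design is for.

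Second, a paired test needs both readings of its pair. Without imputation, anyone missing either one is left out. A person who leaves after week 12 has three post-baseline scans (weeks 4, 8 and 12). Paired tests at those visits could use them, but a week-24 paired test without imputation cannot. If leaving is related to response, the remaining pairs show change that did not happen: improvement if non-improvers leave, worsening if improvers leave. Reminders may reduce the loss, but they do not say how lost readings are analysed.

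At stake is the primary end point, since this is the only named way to judge it.

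**Working it through.** **Inputs from the documents.** 30 per arm; FibroScan at baseline and weeks 4, 8, 12, 16 and 24 in both arms; a paired t test within each intervention. The only planning figure is the sample size, 2 x 30 = 60. It cannot be reproduced, because no alpha, power, effect size, SD or dropout rate is given.

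**Assumptions, none in the documents.** Two-sided 5% test and no true effect. A fraction d (10%, 20% or 30%) leaves after week 12 and loses weeks 16 and 24. The chance p of leaving is logistic in the observed week-12 change, with slope b per SD: mild is b = 0.5 (odds ratio 1.65), strong is b = 1 to 2 (2.7 to 7.4). The correlation between visits is 0.6 throughout (exchangeable), or 0.9 per four weeks (decaying). Bias is in SD of 24-week change; negative means false improvement.

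**Step 1: hand check of the paired test.** For normal data the bias in completers' mean change is

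bias = -r x b x E[p(1-p)] / (1-d),

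where r is the correlation between week-12 and week-24 change. With exchangeable correlation 0.6, r = (1 - 0.6) / (2 x (1 - 0.6)) = 0.5. E[p(1-p)] is found by numerical integration over a standard normal change, with the intercept set to give d.

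- d = 20%, b = 0.5: E[p(1-p)] = 0.154, so bias = -0.5 x 0.5 x 0.154 / 0.8 = -0.048. With 24 pairs the SE is 1/√24 = 0.204, and 0.048/0.204 = 0.235. Rejection rate: Φ(-1.725) + Φ(-2.195) = 0.042 + 0.014 = 5.6%.
- d = 30%, b = 2: E[p(1-p)] = 0.131, so bias = -0.5 x 2 x 0.131 / 0.7 = -0.187. With 21 pairs the SE is 0.218, and 0.187/0.218 = 0.86. Rejection rate: Φ(-1.10) + Φ(-2.82) = 0.136 + 0.002 = 13.8%.

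**Step 2: simulation of the paired test** (10,000 replicates, Monte Carlo SE about 0.2 points at 5%), exchangeable 0.6, non-improvers leave. Bias, then type I error:

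| Dropout | b = 0.5 | b = 1 | b = 2 |
|---|---|---|---|
| 10% | -0.022, 5.0% | -0.044, 5.6% | -0.069, 6.4% |
| 20% | -0.051, 5.9% | -0.088, 7.1% | -0.128, 9.3% |
| 30% | -0.074, 6.0% | -0.129, 8.4% | -0.187, 13.3% |

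This agrees with step 1. If improvers leave, the sign reverses with about the same size (+0.047 to +0.186 at 20% to 30%). With random dropout the bias is within 0.003 SD and type I error is 4.7% to 5.5%. With decaying correlation, 20% to 30% dropout gives -0.063 to -0.249 and 6.3% to 21.6%. A different data model (random intercept and slope) gives about 9% rejection at 20% dropout and 13% to 14% at 30%.

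**Step 3: comparing the arms.** If both arms share the mechanism, completer ANCOVA has bias of at most 0.01 SD and type I error of 4.6% to 5.5%. If only supplement-arm dropout depends on response, and placebo dropout is random at the same rate, completer ANCOVA gives:

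| Correlation, dropout | b = 0.5 | b = 1 | b = 2 |
|---|---|---|---|
| 0.6, 20% | -0.027, 4.9% | -0.053, 5.5% | -0.084, 6.3% |
| 0.6, 30% | -0.041, 4.9% | -0.079, 5.7% | -0.117, 6.9% |
| decaying, 20% | -0.051, 5.3% | -0.086, 6.1% | -0.129, 7.9% |
| decaying, 30% | -0.068, 5.6% | -0.120, 7.5% | -0.181, 10.1% |

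An unstructured repeated-measures model has bias within 0.005 SD and type I error of 4.2% to 4.8% in these settings.

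**Step 4: dropout on the unseen week-24 change**, supplement arm only, correlation 0.6. Across 20% to 30% dropout, ANCOVA bias is 0.080 to 0.307 SD and the model's is 0.061 to 0.241 SD, with type I error of 4.9% to 13.5%. The share removed is 1 - 0.061/0.080 = 24% at the mild end and 1 - 0.241/0.307 = 21% at the strong end. The shift in imputed values that would cancel the remainder is bias / dropout: from 0.087/0.30 = 0.29 SD to 0.165/0.20 = 0.83 SD. The sign depends on who leaves, so a shift analysis must run in both directions.

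**The case against.** The strongest reply is that the serious gap is the missing comparison of arms, and that the repeated-measures model adds little once there is one. Blinding makes a shared dropout mechanism plausible, and then the model adds nothing to completer ANCOVA. With a mild one-arm mechanism and correlation 0.6, ANCOVA's type I error is 4.9%, so there is no inflation. The 10% figure needs decaying correlation, 30% dropout, the steepest slope and dependence in one arm only, all at once. Every driver is assumed, and the reminders push dropout towards the low end. A baseline-adjusted arm comparison with a stated missing-data rule would do most of the work.

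All of that stands as to weight. It does not rescue the paired t test, which makes no arm comparison with or without dropout. Since the scans are already scheduled, the model's extra protection costs little.

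A reader might infer that the trial's conclusion about the supplement carries a false-positive rate of 13% or even 22%. The documents do not support that: those figures describe a within-arm test under assumed strong dropout. Nor does the SAP prescribe a complete-case analysis. It is silent, and complete pairs follow only because no imputation is stated; a paired test after imputation could use the earlier scans.

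**Conclusion.** The point holds, as something the sponsor should change. That the only named analysis of change is within-arm, with no missing-data rule, is plain from the text. The harm from dropout is conditional: nil if dropout is random, small at 10%, and about 0.05 to 0.19 SD with type I error of about 6% to 13% at 20% to 30% under the assumptions above with correlation 0.6.

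Most of the gain comes from comparing the arms. The model's own contribution is confined to dropout that depends on observed response in one arm only. There it removes a completer ANCOVA bias of 0.03 to 0.04 SD (mild, type I error about 5%), 0.05 to 0.12 SD (strong, 5.5% to 6.9%), or up to 0.18 SD (about 10%) if correlation decays. It only partly handles dropout on unseen values. It would be too much to say that the model cures informative dropout, or that these documents show such dropout will occur.

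Confidence is medium, because dropout, correlation and mechanism are all assumed. The remedy also assumes that FibroScan measures the primary end point, which section 1 implies and section 3 does not state.

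**What to change.** In section 3, replace the paired t test as the primary analysis with text such as:

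*All randomised participants are analysed in their assigned arm. FibroScan readings at weeks 4, 8, 12, 16 and 24 are analysed in a mixed model for repeated measures with arm, visit, arm-by-visit, baseline and baseline-by-visit, unstructured covariance and Kenward-Roger or similar small-sample degrees of freedom. If it does not converge, compound symmetry with small-sample-corrected robust standard errors is used. The week-24 arm difference with its 95% confidence interval is the primary estimate. Dropout is reported by arm and visit. In a sensitivity analysis, missing week-24 values are multiply imputed and then shifted in each arm over a range from -1 to +1 SD of 24-week change, and the shift at which the conclusion changes is reported.*

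Keep the paired t tests as descriptive. State that FibroScan measures the primary end point, and what will be done if the planned normality checks fail. Control of multiplicity across the two FibroScan measures is optional and a separate point, as is the handling of readings taken after tablets are stopped.

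**Cost.** New text and modest programming, with no extra visits or scans. The software named ("R software version 2.11.1") should be checked for the small-sample method. The model is more complex at 60 people (5 x 6 / 2 = 15 covariance parameters) and gains little precision. The compound-symmetry fallback leaves 0.02 to 0.05 SD of bias if correlation really decays and only one arm's dropout depends on response.
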